7.2.4 Analysis Periods

To facilitate the analyses based on eDiary data (including eDiary compliance and migraine days), the analyses for safety endpoints, the following analysis periods will be defined.

Table 1. Analysis Periods

Analysis periods	Start date/time	End date/time	Usage
OP	Screening Visit date	LT _T start date – 1 day	To be used to calculate the eDiary compliance, number of migraine days per 4 weeks in this period.
LT _T	Earlier of (1) Baseline Visit date, and (2) study drug start date	Later of (1) Week 52/EOT date, and (2) study drug last dose date	To be used to calculate the eDiary compliance and number of migraine days per 4 weeks or the overall period in the long-term treatment.
Pre-treatment safety		Study drug start date – 1 day for AEs; study drug start date/time otherwise	To be used to assess the safety endpoints prior to study drug treatment.
Treatment safety	Study drug start date for AEs; after study drug start date/time otherwise	[Later of (1) Week 52/EOT date, and (2) study drug last dose date] + 7 days	To be used to assess the safety endpoints of the treatment period.
Follow-up safety	[Later of (1) Week 52/EOT date, and (2) study drug last dose date] + 8 days		To be used to assess the safety endpoints of the follow-up period.

7.2.5 Analysis Visit Windows

According to Section 4.3 of the protocol, the analysis visit windows for efficacy analyses will be defined. Analysis windows for the secondary endpoint will be defined within the OP and LT_T analysis periods that are defined in Section 7.2.4 (See [Table 2](#)[Table 2](#)). The calculation of number of migraine days will be based on the study day as defined in Section [Error! Reference source not found.](#)[7.2.3](#). Analysis windows for the exploratory endpoints will be defined directly as below in [Table 3](#)[Table 3](#).

Table 2. Analysis Windows for Migraine Days

Per 4-week Interval	Analysis Window in the LT _T Analysis Period (Study Day)
Month 1: Week 1 to Week 4	1-28

Month 2: Week 5 to Week 8	29-56
Month 3: Week 9 to Week 12	57-84
Month 4: Week 13 to Week 16	85-112
Month 5: Week 17 to Week 20	113-140
Month 6: Week 21 to Week 24	141-168
Month 7: Week 25 to Week 28	169-196
Month 8: Week 29 to Week 32	197-224
Month 9: Week 33 to Week 36	225-252
Month 10: Week 37 to Week 40	253-280
Month 11: Week 41 to Week 44	281-308
Month 12: Week 45 to Week 48	309-336
Month 13: Week 49 to Week 52	337-end of LTT

Table 3. Analysis Windows for MSQoLQ, MIDAS, PoM, SM, and CGI-c Scale

Scheduled Visits *	Target Day (Based on Study Day)	Analysis Window (Study Day)
Baseline	1	Prior to or on the first dose date
Week 12	84	71-98 #
Week 28	196	183-210 #
Week 40	280	267-294 #
Week 52	364	351- end of LTT
Early Termination	The Early Termination Visit or last post-baseline questionnaire from the early terminated participants	

* The PoM, SM, and CGI-c scale will not be collected at baseline, Week 12 and Week 40.

For early terminated participants, the Week X window end date will be the minimum of (1) Early Termination Date -1 day or (2) Week X analysis window end date, where X is the last Week with Target Day being prior to Early Termination Date.

In [Error! Reference source not found.](#)[Table 3](#), if there are multiple non-missing values fall into a same analysis windows, then the following algorithm will be taken to identify the value for analysis:

1. The value closest to the target day for the visit will be used.
2. If the observations are with equal distance from the target day in absolute value, the one with correct nominal visit label will be used. For example, if two observations fall into the analysis window for Week 28 Visit on Study Days 190 and 202, respectively, the observation that is recorded as Week 28 will be used.
3. If neither 1 nor 2 can identify the observation, then the last value measured is used.

All observations will, however, be included in the listings.

7.3 Study Participants

7.3.1 Participant Disposition

A participant disposition summary table will be provided based on screened participants. The following categories will be summarized in this table:

- Screened participants
- Screen failures and reasons for screen failure
- Enrolled participants
 - Treated participants
 - Participants who completed the treatment
 - Participants who discontinued treatment and reasons
 - Participants who completed the study
 - Participants who discontinued study and reasons
 - Untreated participants
- Not enrolled but treated

In addition, the number and percentage of participants in each analysis set will be summarized and listed based on screened participants.

7.3.2 Protocol Deviations

Based on the FAS, participants with important protocol deviations (PD) will be summarized according to the classification of PDs, with the number and percentage of cases calculated. Participants with PD will be listed in detail.

During the study conduct, PD reporting was updated per TigerMed's latest SOP. PD categories were changed from Major/Minor PDs to Important/Non-important PDs. The previous major PD categories will be converted to Important PD categories based on medical review. For the minor PDs, if the PDs were due to COVID-19, the categories of these minor PDs will be converted to non-important PD categories based on medical review; if the PDs were not due to COVID-19, minor PD categories will be kept and will not be converted to non-important PD categories. Important PDs and PDs due to COVID-19 will be summarized based on the new PD categories. Listings of PDs will be provided with the new PD categories (Important/Non-important) and the previous PD categories (Major/Minor). See [Appendix: Mapping Rule of PD Categories](#).

The details and severity of PDs will be eventually determined at the data review meeting before database lock.

7.3.3 Demographics/Baseline Characteristics

The demographics and baseline characteristics will be descriptively summarized based on the FAS using the method described in Section 7.1, including:

- Age, gender, ethnicity, weight (kg), height (cm), body mass index (BMI; kg/m²), and

history of allergy (yes, no).

Age at informed consent will be calculated. Age (in years) and BMI will be summarized as a continuous variable, and by categories with numbers and percentages. Age will be categorized as <65 vs. ≥ 65 . BMI will be categorized as < 25 vs. ≥ 25 to <30 vs. ≥ 30 .

The demographics and baseline characteristics will be listed.

7.3.4 Migraine History

The migraine history will be descriptively summarized according to the method described in Section 7.1 and be listed based on the FAS, including:

- Age at migraine onset, did the participant experience migraines for at least one year prior to screening (yes vs no), migraine history (years), average duration of untreated migraine attacks (hours), number of moderate to severe migraines per month within last 3 months, primary migraine type (migraine with or without aura), migraine symptoms (headache attacks lasting 4-72 hours, unilateral location, pulsating quality, moderate or severe pain intensity, experience nausea and/or vomiting during headache, experience photophobia and/or phonophobia during headache), Aura symptoms (visual, sensory, speech and/or language, motor, brainstem, retinal, other symptoms).

7.3.5 Medical History

The medical history will be coded using the latest version of Medical Dictionary for Regulatory Activities (MedDRA Version 25.0).

The number and percentage of participants with at least one medical history will be summarized by System Organ Class (SOC) and Preferred Term (PT) based on the FAS. For each participant, multiple medical histories of the same SOC or PT will be counted only once within each SOC and PT. Tables will be presented in descending order based on frequency of each SOC, and then in descending order based on frequency of each PT within a SOC.

Medical histories will be listed by participants.

7.3.6 Prior and Concomitant Medications

Summaries will be performed based on the SS.

Non-study drugs will be coded into Anatomical Therapeutic Chemical Classification System (ATC) codes and preferred drug names using the World Health Organization Drug Dictionary (WHO-DD). For multiple records of the same drug taken by a participant, the drug will be counted only once under each ATC Grade 2 term and/or PT item.

The non-study medication types include:

- Prior medications, including previous and current medications

Prior medications are defined as those taken before study drug, i.e., imputed start or end date < study drug start date. Note that all non-study medications are considered prior for participants with missing study drug start date. Prior medications include the

following subtypes:

- Previous medications, defined as those taken before informed consent, i.e., those with an imputed start or end date < informed consent date.
- Current medications, defined as those taken on or after informed consent and before study drug.
- Concomitant medications, defined as those taken with study drug.

Summaries will be provided for: current prophylactic migraine medications, concomitant prophylactic migraine medications, current medications, and concomitant medications, respectively.

All non-study previous, current, and concomitant medications, including prophylactic migraine medications and other medications, will be listed.

7.3.7 Prior and Concomitant Non-drug Therapies

Non-drug therapies will be categorized into previous, current, and concomitant therapies based on therapy start/end dates using the same criteria as stated in Section 7.3.6 and be summarized using the same method as stated in Section 7.3.6.

A detailed listing of non-drug therapies will be provided based on the SS.

7.3.8 Drug Accountability and eDiary Compliance

The drug accountability will be summarized by the following categories based on the enrolled participants using the method described in Section 7.1:

- At least one kit dispensed
- Did not return any drug
- Ever lost or wasted drugs
- Average number of dispensed tablets (tablets per month) = 4 (weeks)* (sum of total number of dispensed amount - amount dispensed on the latest return date) / ((latest return date – earliest dispense date) /7)
- Average number of returned tablets (tablets per month) = 4 (weeks)* sum of total number of returned amount / ((latest return date – earliest dispense date) /7)
- Average number of tablets lost or wasted (tablets per month) = 4 (weeks)* sum of total number of not used and not returned amount / ((latest return date – earliest dispense date) /7)

Drug distribution and return profiles will be listed.

The compliance of eDiary Migraine records will be summarized by OP and LTT analysis period based on the SS using the following formula:

Compliance in each period = (actual number of eDiary entry days in the period/ number of days in the period) * 100%, where number of days in the period = analysis period end date – analysis period start date + 1 day (see Section 7.2.4).

- The compliance will be summarized using the method described in Section 7.1.
- The number and percentage of participants with $\geq 80\%$, $\geq 90\%$ compliance will also be calculated.

A listing of the compliance will be provided.

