- Return unused study drug for compliance check (at each site visit);
- Return eDiary and review eDiary and BYOD of completion for completeness (at each site visit);

- Daily recording of migraine attacks and their severity by eDiary;
- MSQoLQ Version 2.1 (at Weeks 12, 28, 40, 52, or early termination);
- Migraine PoM for migraine (Week 28 and Week 52 or at early termination);
- Satisfaction with Medication survey (Week 28 and Week 52 or Early Termination);
- CGI-c scale (at Weeks 28 and 52 or early termination);
- MIDAS (at Weeks 12, 28, 40, 52 or early termination).

Upon completion of the Baseline Visit, WOCBP will be provided with urinary pregnancy test kits so that participants can test at home if necessary. When WOCBP participants cannot confirm pregnancy status, a urine pregnancy test must be completed at home before taking study drugs.

During the treatment period, participants have to use the last bottle of study drug before opening a new bottle of study drug. Three wallets of study drug will be dispensed to the participants at each visit of Week 4, Week 8, and Week 12. Study drug will be dispensed at Week 16, Week 28, Week 40 visits as needed, the maximum dispensing limit for each visit is 7 bottles per participant. Study drug will be dispensed at site visits as needed. Dispensing of study drug may also occur at unscheduled visits as needed.

If a participant lacks 6 or more diary reports per month for 2 months (continuous or non-continuous), the participant's continued participation in the study should be terminated due to lack of compliance.

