### **7.4. Treatment Compliance**

Study drug will be dispensed by the responsible study personnel. Drug accountability and compliance check results should be documented in the participant's study records.

Participants should be instructed on the importance of taking the study drug as directed when a migraine attack occurs (mild, moderate, or severe). At site visits, the responsible study personnel will review the use of study drug recorded in the BYOD and the returned study drug to assess treatment compliance. Dose discrepancies reported by BYOD, review of study drug, and information provided by the participant must be documented in the original medical record. Data in BYOD for incorrect or missing doses and migraine headaches will be corrected by the Data Clarification Record or Study Drug Reconciliation Form. The investigator shall inform the participants participating in the study that if it is confirmed that the participants are lack of compliance, the participants will be terminated to continue to participate in the study. During monthly study visits, if a participant's BYOD records a lack of compliance, the study staff should contact the participant and document this contact in the original medical record to identify potential participant loss to follow-up as early as possible.

Investigators should monitor participants for possible abuse of the study drug (participants taking the study drug for non-therapeutic purposes, such as for elevated or excited mental effects). The investigator should also assess study drug accountability discrepancies (e.g., missed study drug, lost study drug, overuse of study drug). In the event of a study drug accountability discrepancy, the investigator should obtain additional information and explanation from the participant.

Potential cases of study drug abuse or overdose (including failure to return study drug for participants who fail to take the study drug as instructed or discontinue treatment) should be recorded in original medical records, and AEs or SAEs should be reported as appropriate. Protocol deviations should be documented in the event of dose errors (e.g., taking more than 1 tablet on a calendar day).

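### The average number of dispensed tablets in SAP 7.3.8 keeps supply handed out after the latest return in the numerator without the matching time, so it is too high for participants with such late dispensing

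*SAP*

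**What the plan says.** SAP 7.3.8 summarises drug accountability in all enrolled participants. The average number of dispensed tablets per month is 4 times a numerator, divided by a time in weeks.

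- The numerator is "sum of total number of dispensed amount - amount dispensed on the latest return date".
- The time is "latest return date – earliest dispense date", divided by 7. The averages of returned tablets and of lost or wasted tablets use the same time.
- One of the listed categories is "Did not return any drug". No rule is given for the averages of these participants.

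On supply, Protocol 4.3.2 says: "Three wallets of study drug will be dispensed to the participants at each visit of Week 4, Week 8, and Week 12". At Weeks 16, 28 and 40 drug is given as needed, up to 7 wallets (Table 1, footnote 8), and none is given at Week 52. Protocol 4.3.2 adds: "Dispensing of study drug may also occur at unscheduled visits as needed". Protocol 4.4 permits courier shipment to participants who cannot attend because of COVID-19, with the sponsor's prior approval. Protocol 6.7 provides for loss to follow-up, and Protocol 7.4 foresees that some participants who discontinue will not return drug.

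**The concern.** A rate needs a numerator and a denominator that cover the same period. The SAP recognises this in part. It removes the supply handed out on the latest return date, because the time in which that supply could be used lies outside the denominator. The same reasoning applies to anything handed out later, but the formula has no term for it.

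The formula is therefore right only if nothing is dispensed after the latest return. The protocol does not ensure that. Unscheduled dispensing and courier supply need not coincide with a return, and a participant can be lost after a later dispensing.

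At stake is the accuracy of one descriptive line in the accountability table. Those participants would show a dispensing rate that is too high for the interval on which it is stated.

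**Working it through.** The documents give no numerical result for this formula, so there is no figure to reproduce. The check is algebra followed by examples.

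**Notation.** L is the latest return date and W the number of weeks from first dispensing to L. B, S and A are the amounts dispensed before, on and after L.

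**Formula as written.** 4 × [(B + S + A) − S] / W = 4 × (B + A) / W.

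**Formula with matching periods.** 4 × B / W.

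**Ratio.** (B + A) / B = 1 + A/B. It equals 1 when nothing is dispensed after L.

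**Inputs.** 3 wallets each at Weeks 4, 8 and 12 (Protocol 4.3.2), and the maximum of 7 wallets at Weeks 16, 28 and 40 (Table 1, footnote 8). Two assumptions are mine: 3 wallets at Baseline, and 3 wallets at an unscheduled dispensing. The documents do not state the number of tablets per wallet, so results are in wallets per 4 weeks. The ratio does not depend on wallet size.

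**Main example.** 3 wallets at Baseline and at Weeks 4, 8 and 12; last return at Week 16, with 7 wallets given that day; 3 unscheduled wallets at Week 22; no later return.

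- B = 3 + 3 + 3 + 3 = 12, S = 7, A = 3, W = 16.
- As written: 4 × (22 − 7) / 16 = 4 × 15 / 16 = 3.75.
- Matching periods: 4 × 12 / 16 = 3.00.
- Ratio: 1 + 3/12 = 1.25, that is +25%.

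**Late unscheduled or courier supply.** Last return at Week 40, 3 wallets at Week 46, no later return.

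- B = 12 + 7 + 7 = 26, S = 7, A = 3, W = 40.
- As written: 4 × 29 / 40 = 2.90. Matching periods: 4 × 26 / 40 = 2.60. Ratio: 1.12.

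**Early loss.** Last return at Week 4, 3 wallets at Week 8 with no return recorded at that visit, then lost.

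- B = 3, S = 3, A = 3, W = 4.
- As written: 4 × 6 / 4 = 6.00. Matching periods: 4 × 3 / 4 = 3.00. Ratio: 2.00.

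**Completer with last return at Week 52.**

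- B = 12 + 7 + 7 + 7 = 33, S = 0, A = 0, W = 52.
- Both versions: 4 × 33 / 52 = 2.54. Ratio: 1.00.

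**Direction against a longer window.** Take 19 wallets before a Week 28 return, 7 on that day and 1 more at Week 29. As written: 4 × 20 / 28 = 2.86. Extending the window to Week 29 and leaving out the wallet given that day: 4 × 26 / 29 = 3.59. So the overstatement holds for the formula's own window and not for every window one might choose.

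**No return at all.** L does not exist, so none of the three averages can be computed under either version.

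**The case against.** The strongest reply is that the formula works for participants who follow the schedule. Unused drug comes back at every site visit and again at Week 52 or early termination, and nothing is dispensed at Week 52. The latest return then follows all dispensing and the error is zero. The documents give no frequency for the other pattern. The 12% dropout in the sample size section does not supply one, since not every dropout has a dispensing after the last return. This stands and limits the reach of the point. It does not make the formula right for those to whom the pattern applies.

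Three stronger readings are tempting, and the documents do not support them.

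- A reader might infer that heavy users, who have no tablets left to bring back, are affected most. That requires a visit with nothing returned to leave no return record, and the CRF layout is not in the documents. Protocol 7.5 also has empty packages recovered. If a return of zero tablets were recorded at Week 52, the formula as written would give the correct 2.54 in the completer schedule.
- A reader might infer that the flaw defeats the checks in Protocol 7.4, which says: "The investigator should also assess study drug accountability discrepancies (e.g., missed study drug, lost study drug, overuse of study drug". Those checks are made at the site, by comparing recorded doses with returned drug for each participant. They do not use this average. The SAP also lists individual dispensing and return profiles and counts participants who ever lost or wasted drug.
- A reader might infer that participants without a return distort the averages. They already have their own category, and SAP 7.1 reports n with every continuous summary, so they would drop out visibly. What is missing is a sentence saying so.

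**Conclusion.** The point holds as a wording error in one descriptive formula. For a participant with any dispensing after the latest recorded return, the average of dispensed tablets is inflated, within the formula's own window, by 1 + (dispensed after)/(dispensed before). The main example gives +25%, and the other two affected schedules give +12% and +100%. These sizes rest on the assumed 3 wallets at Baseline and on the schedules chosen. The +100% case also needs a scheduled dispensing visit that leaves no return record. The number of participants affected cannot be derived from the documents.

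The consequence is small. Participants whose last return is at Week 52 or end of treatment are unaffected. No primary, secondary or exploratory endpoint uses this average. The exposure summaries and the exposure categories in the safety tables come from the administration data in the CRF (SAP 7.5.1).

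**What to change.** In the numerator of the average number of dispensed tablets, subtract *the amount dispensed on or after the latest return date*. Equivalently, define the numerator as the sum of amounts dispensed before that date. Nothing changes for participants with no later dispensing.

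As a minor clarification, add one sentence: the three averages are not calculated for participants with no return date, and the number of such participants is shown. The same sentence can cover a latest return that falls on the earliest dispensing date, where the denominator is zero.

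The cost is one phrase and one sentence in the SAP, with a small program change. No new data collection is needed, so the CRF, already final according to SAP section 1, stays as it is.

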7.4 Efficacy Analyses

Efficacy analyses will be based on the FAS, unless specified otherwise. Summaries will be based on the analysis visit windows (refer to Section 7.2.5.).

7.4.1 Efficacy Analysis of the Secondary Endpoint

The number of migraine days (refer to appendix: the derivation of migraine day) by total and severity of migraine attacks will be calculated for the OP and the overall LTT period as defined in [Table 1](#)[Table 1](#), and each month (i.e., 4-week interval) as defined in [Table 2](#)[Table 2](#).

Analyses will be based on the EAS, ie, participants who have ≥ 14 eDiary days (not necessarily consecutive) within both the OP analysis period and at least one month (4-week interval) in the LTT analysis period. For the assessment timepoints, all values observed after taking standard of care migraine medications (acute or prophylactic) will be used.

The number of migraine days in OP, per 4-week in LTT period, and overall LTT period will be prorated to 28 days to account for days with missing migraine data:

Number of migraine days in the OP

= $28 * (\text{sum of migraine days in the observation analysis period}) / (\text{sum of eDiary days in the observation analysis period})$.

Number of migraine days per month (4-week interval) in the LTT period

= $28 * (\text{sum of migraine days within a 4-week interval}) / (\text{sum of eDiary days within this 4-week interval})$.

Overall LTT

= $28 * (\text{sum of migraine days in the LTT analysis period}) / (\text{sum of eDiary days in the LTT analysis period})$.

Note that, in the above calculations, participants must have ≥ 14 days of eDiary data (not necessarily consecutive) in the OP, each month (4-week interval) in the LTT period; all participants in EAS will be included in the calculation for overall LTT period.

Prorated absolute values (based on above formulas), change and percentage change from OP in migraine days per month (4-week interval) of LTT period and overall LTT period will be summarized descriptively by severity (total; moderate or severe) using the statistics mentioned

in Section 7.1. For the analysis of the percentage change from OP, only participants who have at least one migraine day (absolute, not prorated to 28 days) of appropriate severity in the OP will be included.

In addition, for each 4-week interval in the LTT period, the number and percentage of participants with the migraine days decreased by $\geq 25\%$, $\geq 30\%$, $\geq 50\%$, and $\geq 60\%$ from the OP will be summarized by severity. The number and percentage of participants with the mean number of migraine days in the overall LTT period decreased by $\geq 25\%$, $\geq 30\%$, $\geq 50\%$, and $\geq 60\%$ from the OP will be summarized by severity.

Longitudinal plots will display the mean reduction in the number of migraine days in the LTT period from the OP on the Y-axis and LTT month on the X-axis, by severity. Vertical bars will display 95% CI. Longitudinal plots for the mean number of migraine days in the LTT period will also be displayed using the same format.

The number of migraine days in prorated absolute value, change from OP, percentage change from OP, and percentage reduction categories will be listed.

